6.5 End of Study Visit and Post-study 3-month Follow-up

6.5.1 At the End of Study (EOS) visit, subjects will be asked to complete additional questionnaires in addition to completing regular procedures. These surveys will assess subjects’ experiences over the course of the study including changes in their medical insurance status, access to other health services, changes in their perceptions of PrEP and of their own health, and their opinions on the intervention.

Upon completion, subjects will not be dispensed PrEP and will be discontinued from the study.

Subjects that express the desire to continue PrEP after completing the study will be provided information regarding access and payment strategies.

- 6.5.2 Subjects that complete CCTG 595 will be approached EOS and asked to join a supplement-funded extension, consisting of a one-time phone call follow-up scheduled for 3 months post-study. The purpose of this extension is to examine sexual risk compensation and the impact of transition after cessation of study-provided PrEP.

Written consent will be obtained at EOS; subjects that have already completed their EOS visit will be contacted and verbal consent will be obtained over the phone.

At 3 months post-study, subjects will be contacted over the phone and asked questions regarding their current HIV status, their ability to access and maintain their PrEP regimen after EOS, and their ability to obtain health insurance coverage. If subject is off PrEP and/or has no health insurance, the subject will be asked for their reasons and possible barriers. Subjects will also be asked an abbreviated number of questions from surveys similar to those done during the main study, including measures assessing risk compensation, perceptions of PrEP efficacy, and adherence (if on PrEP).

7.0 TOXICITY MANAGEMENT

The management of medication related toxicities should be undertaken by the local investigators, with guidance available from the protocol team, protocol pharmacist and pharmaceutical sponsor, to ensure the optimal safety and efficacy for the individual subject.

7.1 General Management for Grade 1-4 Events

7.1.1 Grade 1 or 2

Subjects who develop a Grade 1 or 2 adverse event or toxicity may continue TDF/FTC without alteration of the dosage, except as noted below. Persistent grade 1 or 2 toxicity should be discussed with the protocol team. Those subjects experiencing Grades 1 or 2 adverse events which results in discontinuation of the TDF/FTC should continue to be followed on study, but off study medication.

7.1.2 Grade 3

Management of Grade 3 toxicities should be discussed with the protocol team via email. Please refer to the subsequent sections for management of specific events.

In the event that a subject develops a **symptomatic** Grade 3 reaction considered to be TDF/FTC-related, the study drug should be discontinued and the subject should be followed weekly until resolution of the adverse event. Once Grade 3 is resolved the subject should be followed on-study, but off study medication. For subjects with asymptomatic Grade 3 toxicity or laboratory abnormalities, the protocol team should be consulted for possible re-introduction of TDF/ FTC.

7.1.3 Grade 4

Subjects who develop a Grade 4 adverse event or toxicity judged to be TDF/ FTC-related will have the study drug permanently discontinued. For other Grade 4 events, if the toxicity or laboratory elevation is thought not to be due to TDF/FTC, TDF/FTC may be continued and laboratories repeated within 2 weeks (for example for asymptomatic elevation of CPK or triglycerides). If it is not possible for the investigator to discern another causative agent/ condition or if TDF/FTC could be the causative agent, then TDF/FTC must be discontinued. Subjects experiencing Grade 4 adverse events requiring permanent discontinuation of TDF/FTC therapy should be followed weekly until resolution of the adverse event. Once Grade 4 is resolved the subject should be followed on-study, but off study medication.

7.2 Management for Specific Adverse Events

7.2.1 Rash

Grade 1 or 2

TDF/FTC may be continued without interruption. Subjects with a Grade 1 or 2 rash may be treated symptomatically with permitted antipyretic, antihistamine and/or non-steroidal anti-inflammatory medications, but should be monitored closely by the local investigator.

Grade 3 or 4

Grade 3 or 4 rash necessitates that TDF/FTC be held unless the rash is determined to be unrelated to TDF/FTC. The rash should be followed closely for resolution and the subject followed on-study, off study medication.

7.2.2 Nausea and Vomiting

Grade 1 or 2

TDF/FTC may be continued without interruption. Subjects with Grade 1 and 2 nausea or vomiting may be treated symptomatically with permitted oral antiemetic therapies or antiemetic suppositories. Subjects will be instructed to take medications with food.

Grade 3 or 4

Subjects with Grade 3 TDF/FTC-related nausea and vomiting should interrupt TDF/FTC until the toxicity grade returns to Grade ≤ 2 or to baseline and be treated symptomatically. After discussion with the protocol team and if the subject is willing, the TDF/FTC may be resumed when symptoms have resolved. If Grade 3 nausea and vomiting recurs upon the resumption of TDF/FTC despite symptomatic treatment, TDF/FTC should be discontinued. Grade 4 nausea or vomiting will lead to permanent discontinuation of drug. Once resolved, the subject should be followed on-study, but off study drug.

7.2.3 Diarrhea

Grade 1 or 2

TDF/FTC may be continued without interruption. Subjects with diarrhea of any toxicity grade may be treated symptomatically with permitted antimotility agents.

Grade 3 or 4

For grade 3 diarrhea that is unresponsive to antimotility agents and for which an alternative etiology (e.g., infectious diarrhea) is not established, TDF/FTC should be interrupted until resolution of diarrhea to Grade \leq 2 or baseline. If Grade \geq 3 diarrhea recurs upon the resumption of study medications, TDF/FTC should be permanently discontinued. Grade 4 will lead to permanent discontinuation of study medication.

7.2.4 Hyperglycemia

Fasting hyperglycemia of > 110 to 125 mg/dL is considered evidence of impaired glucose tolerance. A fasting blood glucose level above 126 mg/dL is highly suggestive of diabetes mellitus. Subjects with fasting hyperglycemia may continue TDF/FTC at the discretion of the investigator but should be discussed with the protocol team via email. A confirmatory fasting glucose will be obtained within 4 weeks and prior to the institution of medical therapy. Hyperglycemia may be treated with oral hypoglycemic agents or insulin according to standard guidelines. Abnormal glucose levels will be monitored closely, and further laboratory repeats will be at the discretion of the site PI.

7.2.5 AST/ALT Elevations

Grade 1 or 2

TDF/FTC may be continued. Tests should be repeated and reassessed within 2 weeks if AST/ALT results are \geq grade 2

Grade 3

All grade 3 or 4 elevations of AST/ALT should be discussed immediately with the protocol team via email. TDF/FTC may be continued for Grade 3 AST/ALT elevations at the discretion of the site investigator after discussion with the protocol team. Careful assessments should be done to rule out the use of alcohol, non-study medication-related drug toxicity, or viral hepatitis as the cause of the Grade 3 elevation.

Grade 4

TDF/FTC will be permanently discontinued for AST or ALT Grade 4 elevations, and the protocol team will be notified. The subject should have repeated AST or ALT evaluations until the levels have returned to $<$ grade 2 or baseline. Once the AE is resolved, the subject should be

followed on-study, but off study medication.

7.2.6 Creatinine Elevations

TDF/FTC will be discontinued if the creatinine clearance is confirmed to be < 50 mL/min. Subjects should be followed as medically indicated until the creatinine returns to baseline. The protocol team will be notified within 48 hours of any permanent therapy discontinuations due to change in creatinine clearance.

If the serum creatinine increases more than 0.3 from baseline, the level should be repeated in 2 weeks. Elevations in creatinine will be monitored closely, and further laboratory repeats will be at the discretion of the site PI.

7.2.7 Anemia/Neutropenia

Subjects with Grade 3 anemia or neutropenia attributed to TDF/FTC should have all study treatment interrupted until the abnormality returns to Grade \leq 2. Therapy may be resumed after the anemia or neutropenia has returned to Grade \leq 2. If Grade 3 anemia or neutropenia recurs, TDF/FTC will be discontinued, and the protocol team will be notified.

Grade 4 anemia or neutropenia will result in permanent discontinuation of study medication if it is due to TDF/ FTC.

8.0 CRITERIA FOR TREATMENT DISCONTINUATION

8.1 Criteria for Discontinuation from Study

- 8.1.1 Diagnosis of HIV infection.
- 8.1.2 Request by the subject to withdraw.
- 8.1.3 Request of the primary care provider if s/he thinks the study is no longer in the best interest of the subject.
- 8.1.4 Clinical reasons believed life threatening by the study physician, even if not addressed in the toxicity management of the protocol, and can no longer continue in follow up.
- 8.1.5 Subject judged by the investigator to be at significant risk of failing to

comply with the provisions of the protocol as to cause harm to self or seriously interfere with the validity of the study results.

- 8.1.6 At the discretion of the CCTG, FDA, CHRP or pharmaceutical sponsors.
- 8.1.7 Misses two consecutive scheduled visits prior to 48 weeks.
- 8.1.8 Misses one scheduled visit after 48 weeks.

9.0 STATISTICAL CONSIDERATIONS

A formal Statistical Analysis Plan (SAP) will be drafted and finalized prior to database lock. The SAP will contain a more detailed and/or comprehensive presentation of statistical methods, attention to any changes of substance to planned analysis procedures relative to those indicated in the protocol, and is the final authority for all statistical analyses. The following section briefly describes the planned statistical analyses. In case the language in this section differs from the language in the SAP, the SAP takes precedence.

9.1 Primary Endpoints

Adherent to PrEP through 48 weeks is defined as a composite endpoint of continuing on study (made all scheduled visits within window in the 48 week period) and on study medication and greater than or equal to 90% adherent to medication defined by self-report of ≥ 18 of 20 doses of medication on the 5 ACTG adherence questionnaires at weeks 4, 12, 24, 36 and 48. Missing adherence forms will be imputed as no doses taken.

9.2 Secondary Endpoints

- 9.2.1 Adherent to PrEP by FTC measurement at 48 weeks and at the end of study follow-up is defined by attending all scheduled visits and having detectable FTC.
- 9.2.2 Adherent to PrEP in continuous follow up is aggregate percentage of self-reported ACTG days of adherence where missed schedule visits are counted as 0/4 days.
- 9.2.3 Poor adherence is considered those with <90% self-reported adherence by ACTG 4 day survey or if discontinued drug. Subgroup analysis should explore the endpoint for discontinuation for reasons other than quit drug for lack of risk or confirmed adverse event.
- 9.2.4 Safety and tolerability defined as: i) discontinuation of TDF/ FTC for any

toxicity; ii) grade 2 or higher adverse event or laboratory toxicity; iii) serious adverse event; iv) death

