1.0 STUDY OBJECTIVES AND HYPOTHESES

1.1 Study Primary Objective:

CCTG 595 will compare adherence to fixed dose TDF/FTC, between subjects randomized to receive SoC plus text message reminders versus SoC, when used for pre-exposure prophylaxis among MSM at high risk for HIV acquisition.

1.1.1

Hypothesis I

MSM and transgender M to F having sex with men with high risk of HIV acquisition randomized to the iTAB intervention will have higher self-reported adherence to TDF/FTC for PrEP over 48 weeks ('adherent' defined with a composite endpoint of continued retention on PrEP and \geq 90% adherence to TDF/FTC at 48 weeks) compared to MSM that have comprehensive SoC alone.

1.1.2

Hypothesis II

MSM and transgender M to F having sex with men with high risk of HIV acquisition randomized to the iTAB intervention will have higher adherence to TDF/FTC for PrEP over 48 weeks, as measured by having five of five detectable qualitative FTC plasma concentrations at scheduled visits compared to MSM that have comprehensive standard of care alone.

1.2 Study Secondary Objectives:

1.2.1

To compare adherence to TDF/FTC in the iTAB versus SoC in the subjects that remain on PrEP (at 48 weeks and up to 96 weeks of follow up) by the continuous measure of percent days adherent by the cumulative 4 day ACTG and the visual analog scale (VAS) recall in an 'as treated' analysis.

1.2.2

To compare adherence to TDF/FTC in the iTAB versus SoC groups for the duration of the study (up to 96 weeks). Adherence will be compared using the same outcomes as hypothesis I (self-reported to be on drug and 90% adherent) and II (100% detectable FTC at each scheduled visit) as modified intent to treat analysis.

1.2.3

To determine factors associated with poor adherence/lost to PrEP in study participants (outcomes of < 90% adherent on drug at 48 weeks by ACTG 4 day recall or discontinuation of drug). Factors associated with poor adherence to TDF/FTC will include demographics, ongoing

substance use, untreated mental illness, socioeconomic status, low health/HIV and system literacy, fear of disclosure and non-English language.

- 1.2.4 To determine the factors associated with discontinuation of TDF/FTC at any time point including change in perceived and actual risk of HIV acquisition, demographics, ongoing substance use, untreated mental illness, socioeconomic status, low health/HIV and system literacy, fear of disclosure and non-English language.

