Daily dosing reminders will be sent for the first 6 weeks and then continue with reminders for the duration of the study. Both reminder timing and message content can be individualized. The study coordinator will work with the participant to select and refine 10 personal reminders from a list of pre-determined reminders that cover various themes shown to be effective in improving adherence (e.g., social support, loss frame, health gain, etc.) as developed through focus groups and targeted group feedback. These messages can be modified and the patient can choose to create their own reminders if they prefer. The coordinator will work with each participant individually to assure that adherence reminders are sent at times consistent with when the patient typically takes his medication. These reminder times can vary for different days of the week to accommodate for changes in schedule (e.g., 8 M-F, and 10 AM on Sat/Sun). Once the time is identified, the text reminder system is automated. Patients will confirm medication taking via text responses to the personalized reminders. If a participant does not respond on three consecutive occasions, a high alert message (chosen by the participant) will be sent. If the subject does not respond to this message, the study coordinator would initiate phone calls to contact the subject and explore barriers. The coordinator will continue to call the participant every 4 days until the participant re-engages with the iTAB system.

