3.3 FTC Qualitative Plasma Concentration as an Adherence Marker

Adherence to prescribed treatment can be difficult to assess. One objective way to measure recent adherence is to measure plasma drug concentrations. FTC concentrations in plasma remain detectable throughout the dosing interval. Specifically, trough concentrations of FTC are approximately 60 – 70 ng/mL, and range from 10 – 300 ng/mL between subjects [23, 24]. Peak concentrations are approximately 1300 – 1800 ng/mL, and range from 600 to 2500 ng/mL. While many factors contribute to variability in plasma concentrations, such as drug-drug interactions and genetic differences in absorption and excretion, completely undetectable plasma concentrations of FTC are physiologically implausible for patients who are adherent with their regimen. Even with the sources of variability noted above, undetectable concentrations (< 1 ng/mL) would be 60 to over 1000 times less than the expected concentration depending on the time post-dose, and can be justifiably assumed to represent missed doses rather than pharmacokinetic variability. We plan for 400 subjects and in total will have 3467 levels (an average of 8.6 per person). Samples will be stored at each study visit (weeks 4, 12 and every 12 weeks thereafter).

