In the standard study visit, the coordinator will perform HIV testing and blood work, review test results, provide TDF/FTC prescriptions, discuss medication use, adherence, risk reduction and troubleshoot any barriers. The standard behavioral survey will include assessment of TDF/FTC adherence, HIV transmission risk behaviors, substance use, depression scores and other risk behavior details (e.g. sexual partnerships, sexual acts, condom use).

Laboratory Safety Assessments

At follow-up clinic visits, all participants will have a blood drawn for creatinine clearance estimates. A rapid test for HIV will be performed. HIV test results will be provided during the clinic visit. If there are grade 3-4 adverse events (thought to be related to study medication- see toxicity section) or HIV seroconversion is detected, the participant will be called to discontinue TDF/FTC and to come to the clinic as soon as feasible. Any positive rapid test will be confirmed by Western Blot and HIV RNA; CD4 cell count and an HIV genotype for drug resistance will be done. Newly diagnosed HIV subjects will be counseled and be linked to HIV clinical care within the existing clinic or to another provider

designated by the participant. All PrEP-related clinic visits, laboratory testing and TDF/FTC medication will be provided by the study without charge to the subject.

FTC Qualitative Plasma Concentration as an Adherence Marker:

Plasma will be drawn at every visit starting at week 4 for FTC concentrations. Samples will not be run in real time and will not be available for clinical use.

Chlamydia, gonorrhea and syphilis testing

Subjects will have day 0 and every 24-week assessment to include urine and swabs from the rectum and throat for NAT testing for Chlamydia and gonorrhea. Blood will be drawn for RPR. In between visits, subjects will be told to come to the study nurse if they experience symptoms of an STI. They will also be asked if they were tested elsewhere between visits. All new STI cases will be referred to their provider or the Department of Health for treatment. They will be given a card to have filled out documenting treatment given, which they will be asked to bring back to their next study visit. All new STI cases will also be counseled on the need for partner therapy and will suggest that they receive assessment and treatment or partner delivered therapy. STI testing can also occur as an interim visit for high-risk exposure or symptoms suggestive of new STI.

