The primary adherence endpoint will be a binary endpoint (Yes/No) based on DBS samples from two visits (week 12 visit and the last on-drug visit over the 48 weeks). Both visits should have a detectable TFV-DP level >719 fmol/punch (consistent with taking four or more doses per week) to be considered adherent. If the last on-drug visit was at week 12 (i.e. the subject had only one DBS sample), adherence will only be determined by that sample. If a subject discontinued study before week 12 (i.e. had no DBS samples at all), the subject will be considered non-adherent.

Additional Secondary Adherence Endpoints

- Self-reported Adherence: a binary composite endpoint of continued on PrEP and $\geq 90\%$ self-reported adherence to TDF/FTC over 48 weeks. The endpoint will be defined yes if 14 or 15 out of 15 days were reported 'adherent' on the 3-day recall on the clinical assessment form collected at w4, w12, w24, w36, and w48. Note if a subject discontinued the study or missed any visits before w48, those visits will be considered not adherent in the calculation.
- a continuous version of the self-reported adherence measure: defined as percent days that were reported adherent based on the clinical assessment form. In the case where the adherence measure is missing (either due to the subject discontinued PrEP, or missed visit, or other reasons), two approaches will be applied.
 - treat the missing as 'not adherent'. This assumes the worst case (i.e. assume all the missing is related to adherence).
 - ignore the missing. This assumes the best case (i.e. assume all the missing is not related to adherence).
- FTC Adherence: a binary endpoint of having four of four detectable qualitative FTC plasma concentrations (measured at w12, w24, w36, and w48) over 48 weeks. Detectable FTC is defined as a quantitative level of ≥ 0.35 ug/ml consistent with taking a dose in past 24 hours. Note missing will be treated as not detectable.
- Similar outcome as the primary endpoint where we will use the cut-off of ≥ 1246 fmol/punch consistent with taking seven doses per week.
- Proportion of subjects on PrEP at week 48.

Descriptive Analysis

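### The SAP's FTC adherence endpoint omits week 4 without a reason: it requires four of four levels from week 12, where the protocol requires five of five, yet still describes 48 weeks

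*Protocol*

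**What the plan says.** **Protocol.** Hypothesis II (1.1.2), listed under the primary objective, measures adherence over 48 weeks by "five of five detectable qualitative FTC plasma concentrations at scheduled visits". Section 9.2.1, under secondary endpoints, says FTC adherence "is defined by attending all scheduled visits and having detectable FTC". That sentence names no weeks; the schedule comes from elsewhere. Section 6.2.3 states: "Plasma will be drawn at every visit starting at week 4 for FTC concentrations". Section 3.3 and the schedule in 6.1 agree, with plasma banked at week 4, week 12 and every 12 weeks after that. Section 9.6.3 counts a missing FTC level at any time point as undetectable in the strict mITT analysis.

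**SAP.** Section 6 lists FTC adherence among the additional secondary endpoints, as "having four of four detectable qualitative FTC plasma concentrations (measured at w12, w24, w36, and w48) over 48 weeks", with missing levels counted as not detectable. Week 4 is not mentioned. The self-report endpoint in the same list does use week 4.

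**Other drug-level measures.** The SAP's primary TFV-DP endpoint and its version with a higher cut-off use dried blood spots from week 12 and the last on-drug visit. Protocol 6.1 and 6.3.12 begin dried blood spot collection at week 12.

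**The concern.** The two documents define different endpoints for the same hypothesis. Protocol section 9 says that the SAP will attend to changes of substance, and reducing five required visits to four is such a change, but the SAP is silent on it.

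Two things are at stake. First, the rule is more lenient than its description: adherence over 48 weeks can be awarded without any drug-level evidence before week 12. Second, week 4 is the one visit at which the SAP analyses self-report with no drug level beside it. In an open-label trial of a reminder system, an objective check on self-report is worth having, and the sample for it is already collected.

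**Working it through.** **1. Visits to week 48.** Protocol: 4, 12, 24, 36, 48, which is 5 and agrees with five of five. SAP: 12, 24, 36, 48, which is 4.

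**2. The protocol's own count of levels.** Section 3.3 plans 3,467 levels in 400 subjects, stated as 8.6 each; 3467 / 400 = 8.67, so the figure is reproduced up to rounding. Scheduled visits from week 4 to week 96 number nine (4, 12, 24, 36, 48, 60, 72, 84, 96), a ceiling of 9 × 400 = 3,600. Without week 4 the ceiling is 8 × 400 = 3,200, which is below 3,467. Counting scheduled visits only, the planned total cannot be reached unless week 4 is assayed.

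**3. Levels left out.** To week 48: 5 × 400 = 2,000 against 4 × 400 = 1,600. The difference is 400 levels, or 400 / 2000 = 20%.

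**4. Coverage of the first six weeks.** I read the ±14-day window in Protocol 6.1 as applying to each follow-up visit.
- Week 4: 28 ± 14 = days 14 to 42, wholly within six weeks.
- Week 12: 84 ± 14 = days 70 to 98, starting 70 − 42 = 28 days after week 6 ends.

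Drug-level visits within weeks 0-6: protocol 1, SAP 0 (neither FTC nor dried blood spots).

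**5. Can someone who misses week 4 still pass?** Yes. Before week 48, Protocol 8.1.7 removes a participant only after two consecutive missed visits. Someone who misses week 4 alone can attend the other four visits and meet the SAP rule. Under 1.1.2 and 9.2.1 the same person is non-adherent.

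**6. How far the two rules differ.** No document gives a detection rate per visit, so this is illustration only. Assume independent visits with equal detectability *p*; the pass rates are then p⁵ and p⁴.

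| p | five of five | four of four | difference |
|---|---|---|---|
| 0.70 | 0.168 | 0.240 | 0.072 |
| 0.80 | 0.328 | 0.410 | 0.082 |
| 0.90 | 0.590 | 0.656 | 0.066 |
| 0.95 | 0.774 | 0.815 | 0.041 |

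Without those assumptions, the difference is the share of participants who pass all four later visits but not week 4. It cannot exceed the week-4 failure rate.

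**7. The cut-off.** Protocol 10.1 treats FTC as present at 1 ng/mL or more. The SAP requires at least 0.35 µg/mL, and 0.35 × 1000 = 350 ng/mL. Protocol 3.3 gives troughs of about 60-70 ng/mL, ranging from 10 to 300. The whole stated trough range therefore lies below the SAP's threshold and above the protocol's.

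**The case against.** **Authority.** Protocol section 9 makes the SAP the final authority on analysis. Four visits from week 12 also match the dried blood spot schedule, which is a plausible though unstated reason. This stands in part: the sponsor may choose a four-visit endpoint. But the precedence sentence concerns differences from section 9, Hypothesis II sits in section 1, and precedence does not turn a rule for weeks 12-48 into a test of a 48-week hypothesis.

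**Rank.** This is one of several additional secondary endpoints, and the primary could not use week 4 because no dried blood spot is taken then. That stands and limits the weight of the point.

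**Stronger readings that the documents do not support.**
- *That the SAP skips the only phase with daily reminders.* Protocol 3.2 says "Daily dosing reminders will be sent for the first 6 weeks", then has reminders continue throughout the study without giving a frequency. Daily sending is explicit only for six weeks; nothing says that it stops.
- *That a large block of follow-up goes unmeasured and week 4 would fill it.* By the SAP's own description, a level at its cut-off reflects a dose in about the last day. Week 4 adds one time point, not coverage of weeks 0-12.
- *That a planned test of an early effect is lost.* The stated hypotheses concern 48 weeks, and no document gives a week-4 rate from which to compute power.
- *That self-report cannot be checked against FTC.* It can, at four of the five visits.
- *That restoring week 4 alone restores Hypothesis II.* It does not, given the change of cut-off.

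**Conclusion.** The contradiction holds and should be corrected. The SAP uses four of the protocol's five FTC visits to week 48, keeps a 48-week description and gives no reason. A participant without FTC at week 4, or absent then, can be classed as adherent; whether that happens depends on all four later levels reaching the cut-off. No drug-level measure in the SAP falls in the first six weeks, although week-4 self-report is analysed.

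The effect on the proportion classed as adherent cannot be fixed from the documents. Under independence and equal detectability of 0.70 to 0.95, it is about 4 to 8 percentage points, in the direction of more participants passing. The gap lies in the analysis, not in collection, and the primary endpoint is not touched.

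**What to change.** In SAP section 6:
- Restore week 4 to the FTC endpoint: five of five at weeks 4, 12, 24, 36 and 48, with missing levels counted as not detectable. Add week 4 to the by-visit FTC summary, using the banked plasma.
- If the four-visit version is kept, label it weeks 12-48, state why week 4 is omitted, and report it alongside the five-visit version as a sensitivity analysis.
- Reconcile the FTC cut-off with Protocol 10.1, or report the five-visit endpoint at the protocol's detection limit, before describing it as the test of Hypothesis II.

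Cost: SAP wording and up to about 400 assays on stored samples, which Protocol 3.3 already planned. The proportion classed as adherent will be somewhat lower.
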